Patients who discontinued the administration	If the last date of the final administration of this drug corresponds to following conditions, the patients are deemed to be those who discontinued the administration.

Name of data	Derivation and calculation method
	
Patients who started to receive this drug by August 15, 2013: The start date of the initial administration + less than 1064 days
 
Patients who started to receive this drug between August 16, 2013 and August 15, 2014: The start date of the initial administration + less than 700 days
 
Patients who started to receive this drug between August 16, 2014 and August 15, 2015: The start date of the initial administration + less than 350 days

Presence or absence of reasons for discontinuation	
If patients correspond to those who discontinued the administration and there is at least one check mark in any “Reasons for discontinuation” boxes in “Discontinuation of the survey” section in the survey sheet, the patients are deemed as having reasons for discontinuation and if no description is found in the “Reasons for discontinuation” box in the survey sheet of patients defined as those who discontinued the administration, such patients are defined as patients whose reason for discontinuation is “unknown or not described reason”.

Patients who continue to participate in the survey	
Patients who do not correspond to those who discontinued administration are deemed as patients who continue to participate in the survey.

Presence or absence of complications	
If there is a check mark in a box for complication in “patient information” in survey sheet, such patients are deemed to have complication, and if a column for “presence or absence of complications” is not completed and cannot be assessed, whether patients have complication or not is deemed as unknown or not described, and in any other situations, patients are deemed to have no complication.

Presence or absence of medical history	
If there is a check mark in a box for medical history in “patient information” in the survey sheet, patients deemed to have medical history, and a column for “presence or absence of medical history” is not completed and cannot be assessed, whether patients have medical history or not is deemed as unknown or not described, and in any other situations, patients are deemed to have no medical history.

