Medical history Presence or absence of other conditions	Patients who had data indicating presence or absence of medical history of other conditions in “161207 medical history (FIX) CRO” are deemed to have other conditions, and patients without such data are deemed to not have other conditions.
Complications Presence or absence of hepatic function disorder	Patients who had data indicating presence or absence of liver disorder in “161207 complication (FIX) CRO” are deemed to have hepatic function disorder, and patients without such data are deemed to not have hepatic function disorder.
Complications Presence or absence of renal impairment	Patients who had data indicating presence or absence of renal disorder in “161207 complication (FIX) CRO” are deemed to have renal impairment, and patients without such data are deemed to not have renal impairment.
Complications Presence or absence of circulatory disturbance	Patients who had data indicating presence or absence of renal disorder in “161207 complication (FIX) CRO” are deemed to have circulatory disturbance, and patients without such data are deemed to not have circulatory disturbance.
Complications Presence or absence of hematologic disorder	Patients who had data indicating presence or absence of hematologic disorder in “161207 complication (FIX) CRO” are deemed to have blood disorder, and patients without such data are deemed to not have hematologic disorder.
Complications Presence or absence of respiratory disorder	Patients who had data indicating presence or absence of respiratory disorder in “161207 complication (FIX) CRO” are deemed to have respiratory disorder, and patients without such data are deemed to not have respiratory disorder.

Name of data	Derivation and calculation method
Complications Presence or absence of other conditions	
Patients who had data indicating presence or absence of complication classified into other detailed classification (diabetes mellitus, gastrointestinal disorder, osteoporosis, malignant tumour, and collagen disorder, and others) in “161207 complication (FIX) CRO” are deemed to have other conditions, and patients without such data are deemed to not have other conditions.
 
In addition, if there is applicable data for Presence or absence of any conditions by “complications including other detailed classification”, patients are deemed as having such conditions and those without such data, they are deemed to not have such conditions.

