Presence or absence of history of allergy	
If there is a check mark in a box for history of allergy in “patient information” in survey sheet, such patients are deemed to have allergy, and if there is a check mark in a box for “unknown about allergy”, whether patients have allergy is deemed as unknown, and if a column for “presence or absence of allergy” is not completed and in any other situations, patients are deemed to have no history of allergy.

Patients with hepatitis B viral infection	
Patients with description as “hepatitis→ viral” in “complication” and “Type B” in “hepatitis virus carrier” in “patient information”, are deemed to be patients with hepatitis B infection. In addition, patients have events corresponding to MedDRA PT code described in “161207 Hepatitis B (FIX) CRO” are deemed to have hepatitis B infection.

Presence or absence of smoking habit	
If there is a check mark in a box for presence or absence of smoking habit in the survey sheet, patients are deemed to have smoking habit. If there is a check mark in a box for absence of smoking habit in the survey sheet, patients are deemed to have no smoking habit. If there is a check mark in a box for unknown about smoking habit in the survey sheet, whether patients have smoking habit or not is deemed as unknown. If a column for “smoking habit” is not completed, whether patients have smoking habit or not is deemed as not described.

Patients in whom deviation from rules for administration of this drug is noted	
Patients who receive this drug at the dose other than “160 mg→80 mg→40 mg/2 weeks”, “only 160 mg”, or “160 mg→80 mg/2 weeks”, deviation is deemed to have occurred.

Presence or absence of self-administration	
If there is at least one check mark in a column for “Self-administration” in “Administration status” in the survey sheet, the patients are deemed to do self-administration. In any other situations, patients are deemed not to do self-administration.

Presence or absence of self-administration error	
If there is a check mark in a box for “self-administration error was present” in the survey sheet, self-administration error is deemed to be present, and if there is a check mark in a box for “self-administration error was absent”, self-administration is deemed to be absent.
 
In addition, regardless of presence or absence of check mark in

Name of data	Derivation and calculation method

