BMI	Younger than 18.5 years, 18.5 years or older and younger than 25 years, 25 years or older and younger than 30 years, 30 years or older, unknown
Smoking habit	Absent, present, unknown, not described
Disease duration (years)	Shorter than 2, 2 or longer and shorter than 5, 5 or longer and shorter than 10, 10 or longer, unknown/not described
Reasons for use	Gastro-intestinal Behcet disease, other conditions, unknown, not described
Diagnostic classifications of Behcet disease	Complete type, incomplete type, suspected, others, unknown/not described
Main symptoms of Behcet disease	Recurrent oral mucosa aphthous ulcer, cutaneous symptoms, eye symptoms, ulcer of vulva
Evaluation of main symptoms of Bechet disease	0,1,2,3 Recurrent oral mucosa aphthous ulcer Cutaneous symptoms (erythema nodosum, subcutaneous phlebitis, folliculitis-like skin eruption, acne-like skin eruption) Ulcer of vulva Eye symptoms
Presence or absence of eye symptoms of	There is no symptom: Point for evaluation of main symptoms of Bechet disease is 0

data	Method of dividing hierarchy
Bechet disease	There are any symptoms: Points for evaluation of main symptoms of Bechet disease are 1,2,3 Unknown/not described: Other than above situations
Accessory symptoms of Bechet disease	Arthritis without deformity or rigidity, epididymitis, gastrointestinal lesions characterized by ulcer of ileocecum, vascular lesion, moderate or higher degree central nervous lesion
Presence or absence of accessory symptoms of Bechet disease	There are any symptoms: there are check marks in boxes for each accessory symptom There is no symptom: Other than above
History of allergy	Absent, present, unknown, not described
Tuberculin test or IGRA test	Not implemented, implemented, unknown, not described
HBs antigen	Not implemented, implemented, unknown, not described
HBs antibody	Not implemented, implemented, unknown, not described
HBc antibody	Not implemented, implemented, unknown, not described
HBV-DNA quantitative	Not implemented, implemented, unknown, not described
Complications	Absent, present, unknown, not described
Detailed classification of complications	Liver disorder, renal disorder, circulatory disorder, blood disorder, respiratory disorder, others
Other classifications of complications	Diabetes mellitus, gastrointestinal disorder, osteoporosis, malignant tumour, collagen disorder, others
Medical history	Absent, present, unknown, not described

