**“2.9 Incidence of adverse reactions (serious adverse reaction and adverse reaction) by patient characteristics”**

Patients included in analysis: Patients included in safety analysis

Objective of analysis: Incidence of adverse reactions should be shown by patient characteristics and factor analysis should be conducted.

Analysis items: In patients in whom adverse reactions occurred in the period subject to safety analysis, the number of all the patients, the number of patients with serious adverse reactions, and rate of these patients to those included in analysis, the number of the patients with adverse reactions and rate of these patients to those included in analysis, and test provided for the adverse reactions (Fisher’s exact test for nominal scale factors, and Mann-Whitney u test for ordinal scale factors) should be calculated by following patient characteristics:

Notes: Patient characteristics are as follows: Age (years), sex, disease duration (years), complication, hepatic function disorder as complication, renal impairment as complication, medical history, allergy history, smoking habit, self-administration as administration status of this drug, previously used drug/previous treatment, biological preparation adalimumab as previously used drug, biological preparation infliximab as previously used drug, steroid as previously used drug, immunomodulative drug as previously used drug, immunosuppressive drug as previously used drug, oral adrenocortical steroid as concomitant drug, oral mucosa recurrent aphthous ulcer as main symptoms of Behcet disease other than gastrointestinal symptoms, cutaneous symptoms as main symptoms of Behcet disease other than gastrointestinal symptoms, eye symptoms as main symptoms of Behcet disease other than gastrointestinal symptoms, ulcer of vulva as main symptoms of Behcet disease other than gastrointestinal symptoms, arthritis without deformity or rigidity as accessory symptoms of Behcet disease other than gastrointestinal symptoms, epididymitis as accessory symptoms of Behcet disease other than gastrointestinal symptoms, vascular lesion as accessory symptoms of Behcet disease other than gastrointestinal symptoms, moderate or higher degree central nervous lesion as accessory symptoms of Behcet disease other than gastrointestinal symptoms, diagnostic classification of Behcet disease, days until the last date of the administration, and mean daily dose.

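### Patients with a blank complication column are unknown on the parent item but coded as definite negatives for hepatic and renal disorder; the presence trigger in these rows and the smoking row is also miswritten

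*SAP*

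**What the plan says.** All the derivations are in SAP section 10.1.

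- **Parent complication item.** A tick means complication present. If the column is not completed and cannot be assessed, "whether patients have complication or not is deemed as unknown or not described".
- **Hepatic flag.** The trigger is "Patients who had data indicating presence or absence of liver disorder in" the complication file supplied by the CRO. Such patients "are deemed to have hepatic function disorder, and patients without such data are deemed to not have hepatic function disorder".
- **Renal flag.** It has the same structure: patients with data "are deemed to have renal impairment, and patients without such data are deemed to not have renal impairment".
- **Detailed history flags** (tuberculosis, malignant tumour and others). These use the same wording with a medical history file.
- **Smoking.** The first sentence concerns a tick in "a box for presence or absence of smoking habit in the survey sheet, patients are deemed to have smoking habit". The second makes an absence tick a non-smoker: "If there is a check mark in a box for absence of smoking habit in the survey sheet, patients are deemed to have no smoking". Unknown and not-described branches follow. Section 11 lists the levels as: "Smoking habit Absent, present, unknown, not described".

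Sections 9.2 and 9.5 exclude unknown or not-described patients from tests. Tables 2.9 (adverse reactions) and 3.4 (response) test overall complication, hepatic disorder and renal impairment, and also "allergy history, smoking habit, self-administration as administration status of this drug". Tables 2.13.1 and 2.14.1 split adverse reactions by the hepatic and renal flags.

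**The concern.** The parent and child flags treat the same missing information in opposite ways. A patient with nothing in the complication column is unknown for any complication, yet known not to have liver disorder or renal impairment. Table 2.9 would drop this patient from the complication test and count the patient as a negative in the hepatic and renal tests a few lines later. Patients with hepatic or renal disorder are a special-population item in section 5.1, and section 3.1 says the results support regulatory reporting and the reassessment application. The comparison group in those tables should therefore be patients known to be free of the condition.

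The second problem is the wording of the trigger. Read literally, the hepatic, renal and detailed history flags are set to present by any entry about the condition, including an entry that it is absent. For smoking, an absence tick satisfies two rules with opposite results, and no precedence is stated.

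**Working it through.** The SAP gives no prevalence, blank rate or sample size for these flags, so there is no figure to reproduce. The check is one of logic, with illustrations on assumed inputs.

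**1. One patient followed through the rules.** The complication column is blank and the CRO file has no entry.

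| Item | Coded as | In the tests of Tables 2.9 and 3.4? |
|---|---|---|
| Complication (parent) | unknown/not described | No (9.2, 9.5) |
| Hepatic function disorder | does not have | Yes, as a negative |
| Renal impairment | does not have | Yes, as a negative |

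This result does not depend on the layout of the CRO file. It follows from the no-data branch alone.

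**2. Share of the absent group with unknown status.** Let h be the prevalence of liver disorder among patients with a completed column (assumed 10%) and m the share of blank columns (assumed 5-20%).

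Share = m / [(1 - h)(1 - m) + m]

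- m = 0.05: 0.05 / (0.855 + 0.05) = 5.5%
- m = 0.10: 0.10 / (0.81 + 0.10) = 11%
- m = 0.20: 0.20 / (0.72 + 0.20) = 22%

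Unknown status is not the same as wrong status. If blank patients also have 10% liver disorder, the truly affected share of the absent group is hm / [(1 - h)(1 - m) + m]. That is 0.005/0.905 = 0.6% at m = 0.05 and 0.02/0.92 = 2.2% at m = 0.20. With assumed adverse-reaction rates of 40% in affected and 20% in unaffected patients (ratio 2.0), the absent-group rate becomes 20% + 0.6% × 20% = 20.1%, or 20% + 2.2% × 20% = 20.4%. The ratio becomes 1.99 or 1.96. The dilution is small if columns are blank at random. It is not bounded in this way if incomplete sheets also differ in how adverse reactions or response were reported.

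**3. Literal reading of the presence-or-absence trigger.** Let p be true prevalence and a the share of unaffected patients whose absence is recorded in the file. Flagged share = p + (1 - p)a; truly affected among flagged = p / [p + (1 - p)a]. With p = 10% and the same 40% and 20% rates:

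| a | Flagged | Truly affected among flagged | Observed ratio (true 2.0) |
|---|---|---|---|
| 0 | 10% | 100% | 2.0 |
| 0.25 | 32.5% | 31% | 1.31 |
| 0.5 | 55% | 18% | 1.18 |
| 1 | 100% | 10% | no comparison group |

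For example, at a = 0.25: 0.10 + 0.90 × 0.25 = 0.325; 0.10/0.325 = 0.31; (0.31 × 40% + 0.69 × 20%) / 20% = 1.31. Everything depends on a, which the SAP does not give. At a = 0 there is no effect.

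**4. Smoking.** An absence tick meets the first sentence (smoker) and the second (non-smoker). The second sentence and the separate absent level in section 11 have a purpose only if the first sentence refers to the presence box.

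**The case against.** Section 9.1 allows item-specific completion rules in Chapter 10, and coding no data as does not have is such a rule. Section 11 gives the detailed complication items no unknown level; that class is held at the parent. This shows the rule is deliberate, but it does not remove the conflict: the parent and child are tested side by side in the same tables with different patients left out. These are also exploratory factor screens without multiplicity adjustment, so no primary conclusion depends on them. That limits the consequence.

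On the trigger, the objection is stronger. Each row is named for presence or absence of the item, and the label seems to have been carried into the rule. The same idiom appears where only present can be meant, for example in the row for previously used drug/previous treatment and in the adverse-reaction item of Table 2.3. Table 2.3 also counts complications as coded diagnoses, with 0 if there are none, which suggests that the CRO file lists only conditions that are present.

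A reader might infer that every recorded absence becomes a presence, that nearly all patients would be reported as smokers, and that the tested history factors are corrupted. The documents do not support this. The smoking row has its own sentence for non-smokers, the file layout is not shown, and the tested history factors (overall medical history and allergy history) are triggered by a tick for the condition itself. The detailed history flags share the wording but are not tested in Table 2.9 or 3.4.

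**Conclusion.** The parent-child conflict stands without any assumption about the CRO files: patients with blank complication columns are unknown on one tested factor and negatives on two others, and they sit in the absent columns of Tables 2.13.1 and 2.14.1. On the assumed inputs they make up about 6-22% of the absent group for liver disorder. The true figure could be lower or higher, since neither the blank rate nor the prevalence is given. If columns are blank at random, the resulting bias is slight.

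The trigger wording is wrong as written in the smoking, detailed complication and detailed history rows. For smoking it is a contradiction whose intended resolution is clear from the text. For the hepatic and renal flags it would matter only if the file holds negative entries, which cannot be told from the SAP. Actual misclassification of the tables by this route is not shown.

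**What to change.** 1. In the smoking row and the detailed complication and history rows of section 10.1, let only a tick or record of presence set the flag.
2. Code patients who are unknown/not described on the parent complication (or medical history) item as unknown/not described on its child flags. All others without a record of the condition remain negatives. Add the unknown level to the detailed items in section 11.
3. Leave these patients out of the hepatic and renal tests in Tables 2.9 and 3.4, as sections 9.2 and 9.5 already require for unknowns, and show them separately in Tables 2.13.1 and 2.14.1.
4. State whether the CRO complication and history files can contain negative entries.

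The cost is a few lines of wording and a small change to derivation code, with no new data. The downside is a slightly smaller absent group and one extra column in two tables.

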The last date of the final treatment with this drug	
Of dates described in “Administration status of this drug” in survey sheet, records corresponding to following conditions should not be used for analysis.
 
Records of patients who started to receive this drug by August 15, 2013: The start date of the initial treatment with this drug + 1092 days < the start date
 
Records of patients who started to receive this drug between August 16, 2013 and August 15, 2014: The start date of the initial treatment with this drug + 728 days < the start date
 
Records of patients who started to receive this drug between August 16, 2014 and August 15, 2015: The start date of the initial treatment with this drug + 364 days < the start date
 
Of the last date of the treatment complemented by following [1] to [4], the latest date should be the last date of the final treatment with this drug.
 
[1] Data should be sorted by the start date of the treatment, separate volume, and the number of the cycle of treatment described in “Administration status of this drug” in that order.
 
[2] The start date of each data should be complemented at the last date of the initial and second treatment with this drug.
 
When a date is described in the section for the last date of the third or subsequent treatment, and there is no check mark in “Ongoing” box so that last date of the treatment can be

Name of data	Derivation and calculation method

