#### “2.5 List of occurrence status of adverse reactions by presence or absence of self-administration”

Patients included in analysis: Patients included in safety analysis

Objective of analysis: Occurrence status of adverse reactions by presence or absence of self-administration is shown.

Analysis items: Following items should be aggregated by presence or absence of self-administration in adverse reactions that occurred in the period included in safety analysis.

The number of patients included in the survey, the number of patients in whom adverse reaction occurred, the number of adverse reactions, the number of patients in whom

adverse reactions occurred and rate of these patients to those included in analysis by types of adverse reactions (SOC, PT) should be calculated.

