#### “3.4 Aggregation of efficacy by patient characteristics”

Patients included in analysis: Patients included in efficacy analysis

Objective of analysis: As primary survey item, efficacy ratio in level of improvement at the last follow-up for factor analysis.

Analysis items: The number of patients included, the number of responding patients regarding level of overall improvement (significant improvement and improvement) and rate of these patients to those included in analysis, the number of patients who showed ineffectiveness in level of overall improvement and rate of these patients to those included in analysis, and test provided for effectiveness (Fisher’s exact test for nominal scale factors, and Mann-Whitney u test for ordinal scale factors) were calculated by following patient characteristics.

Notes: Patient characteristics are as follows:

Age (years), sex, disease duration (years), complication, hepatic function disorder as complication, renal impairment as complication, medical history, allergy history, smoking habit, self-administration as administration status of this drug, previously used drug/previous treatment, biological preparation adalimumab as previously used drug, biological preparation infliximab as previously used drug, steroid as previously used drug, immunomodulative drug as previously used drug, immunosuppressive drug as

previously used drug, oral adrenocortical steroid as concomitant drug, oral mucosa recurrent aphthous ulcer as main symptoms of Behcet disease other than gastrointestinal symptoms, cutaneous symptoms as main symptoms of Behcet disease other than gastrointestinal symptoms, eye symptoms as main symptoms of Behcet disease other than gastrointestinal symptoms, ulcer of vulva as main symptoms of Behcet disease other than gastrointestinal symptoms, arthritis without deformity or rigidity as accessory symptoms of Behcet disease other than gastrointestinal symptoms, epididymitis as accessory symptoms of Behcet disease other than gastrointestinal symptoms, vascular lesion as accessory symptoms of Behcet disease other than gastrointestinal symptoms, moderate or higher degree central nervous lesion as accessory symptoms of Behcet disease other than gastrointestinal symptoms, diagnostic classification of Behcet disease, days until the last date of the administration, and mean daily dose.

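### Self-administration is an ever-ticked flag but is treated as a fixed patient characteristic, so Tables 2.5, 2.9 and 3.4 can show differences that self-injection did not cause

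*SAP*

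**What the plan says.** Section 10.1 of the SAP sets the flag to present on this condition: "If there is at least one check mark in a column for “Self-administration” in “Administration status” in the survey sheet". For everyone else, blank entries included, it says: "In any other situations, patients are deemed not to do self-administration". Administration status holds several dated records per patient, because the same section gives a sort order for them: "Data should be sorted by the start date of the treatment, separate volume, and the number of the cycle of treatment". One tick on a late record therefore classifies the patient for the whole survey.

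The flag is used in three places.

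- **Table 2.5** (section 13.2): "Following items should be aggregated by presence or absence of self-administration in adverse reactions that occurred in the period included in safety analysis". It reports counts and rates by system organ class and preferred term, with no test.
- **Table 2.9** (section 13.2): "self-administration as administration status of this drug" appears in the list of patient characteristics, and the method is "Fisher’s exact test for nominal scale factors".
- **Table 3.4** (section 13.3): the same list and tests, with response as outcome: "As primary survey item, efficacy ratio in level of improvement at the last follow-up for factor analysis".

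Section 10.2 makes patients, not person-time, the denominator of incidence. Section 2 ends the safety window at 392, 756 or 1120 days for the three cohorts, and 28 days after the last dose for patients who stop. Section 11 has classes for patients who stop after one or two doses. In these three tables nothing compares the date of a ticked record with the onset of a reaction or the date of the response assessment.

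**The concern.** Sex and disease duration are known at the first dose. Ever having self-injected is not: a patient has to stay on the drug until it happens. Grouping patients by a later event while counting outcomes from day 1 has three consequences.

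1. Patients who stop early, for a reaction or for insufficient effect, tend to fall into the absent group (immortal-time bias).
2. Patients in the present group stay on treatment longer, so they have more time in which a reaction can be recorded.
3. Reactions that came before the first self-injection are credited to self-injection.

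The first and second push the safety comparison in opposite directions. In Table 3.4 reactions are not the outcome. There, patients who leave for insufficient effect have less chance of being ticked, so response itself helps to decide who is in the present group.

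Factors that contribute to safety and efficacy are a stated objective (section 4.1), and section 3.1 sends results to the regulator for reassessment. Significant characteristics in Table 2.9 also trigger a further table by seriousness, so a spurious result would be carried forward.

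**Working it through.** The SAP states no figure on this point, so there is nothing to reproduce. The check is a simulation in which self-injection affects nothing.

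**From the SAP:** the ever/never rule, patient denominators, the window of last dose plus 28 days, follow-up of 52, 104 or 156 weeks, and a two-sided 5% level (section 9.6).

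**Assumed, because the SAP is silent** (section 4.3 leaves the number of patients undecided): follow-up of 12, 24 or 36 months with equal probability; hazards per month of 0.02 for a first reaction, 0.01 for stopping for insufficient effect and 0.01 for other stopping; 70% would self-inject; mean delay 0, 1, 3 or 6 months; 0% to 80% of reactions end treatment; N = 200 or 400; 1,500 runs per setting. A responder is a patient who has not stopped for insufficient effect.

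**Anchor.** With no delay and no reaction ending treatment, expected response is 1 minus the mean over F = 12, 24, 36 of 0.5 × (1 - exp(-0.02F)) = 1 - (0.107 + 0.191 + 0.257)/3 = 0.815. The simulation gives 81.5% to 81.7%.

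**Results.** Percentages are self v not self at N = 400, with the difference in points. Rejection is for N = 200 / 400.

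| Mean delay | Reactions ending treatment | Reactions | Rejection | Response | Rejection |
|---|---|---|---|---|---|
| 0 | 0 to 80% | within 0.3 points | 4% to 5% | within 0.3 points | 3% to 5% |
| 1 month | 0% | 31.2 v 29.4 (+1.8) | 4.6 / 4.9% | 82.1 v 80.2 (+1.9) | 6.5 / 6.9% |
| 1 month | 80% | 30.2 v 31.7 (-1.5) | 4.1 / 6.3% | 85.1 v 83.6 (+1.5) | 5.0 / 6.3% |
| 3 months | 0% | 32.2 v 27.9 (+4.3) | 7.8 / 13.0% | 83.4 v 78.2 (+5.2) | 13.7 / 22.2% |
| 3 months | 50% | 30.3 v 31.2 (-0.9) | 4.7 / 4.1% | 84.9 v 81.0 (+3.9) | 9.3 / 15.8% |
| 3 months | 80% | 29.2 v 33.3 (-4.1) | 7.5 / 11.7% | 85.9 v 82.5 (+3.4) | 7.9 / 13.6% |
| 6 months | 0% | 33.4 v 26.5 (+6.9) | 15.3 / 28.5% | 84.5 v 77.2 (+7.3) | 22.6 / 43.0% |
| 6 months | 50% | 30.2 v 31.2 (-1.0) | 4.2 / 4.8% | 85.8 v 80.1 (+5.7) | 15.5 / 31.4% |
| 6 months | 80% | 28.4 v 33.6 (-5.2) | 10.9 / 19.1% | 86.7 v 82.1 (+4.6) | 11.6 / 22.7% |

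At a 6-month mean delay, 7% to 27% of patients with a reaction in the self-administration group had it before their first self-injection.

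**Second set of assumptions.** 30% first-reaction risk and 15% stopping for insufficient effect over 364 days; 70% switch, at a time uniform over days 14 to 180; response in 75% of patients who do not stop for insufficient effect.

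- All patients followed 364 days, half of reactions ending treatment: reactions 27.6% v 33.8% (-6.2 points), rejection 14%, 19% and 29% at N = 200, 300 and 500. Response 67% v 60%, rejection 14%, 20% and 31%.
- Same, with 364, 728 and 1092 days in equal shares: reactions about 43% v 46%, rejection 6% (N = 200) and 7% (N = 500).
- Mixed follow-up, N = 300: the reaction difference runs from +4.5 points (no reaction ends treatment) to -6.8 points (80% do). Response favours self-injection by about 4 to 7 points, rejection 8% to 20%.
- Switching complete by day 56: rejection 4% to 10%.

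**Effect of dating the exposure.** Splitting time at the first self-injection gives a rate ratio of 0.99 to 1.01 in every setting of the first set. In the second set (364 days), rejection is 5.2% (N = 200) and 4.2% (N = 500), against 15.7% and 30.5% for the SAP rule in the same runs. This assumes exact switch dates and covers reactions only.

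**The case against.** The bias needs a delay before self-injection, and the SAP gives no start times. If patients self-inject from the first doses, the tests keep their level. Every other driver is assumed too. Table 2.5 makes no test. In Tables 2.9 and 3.4 the flag is one of 28 factors screened one at a time, section 9.5 disclaims multiplicity, and no primary survey item depends on it. The same criticism applies to concomitant steroid. All of this stands. It limits the size and weight of the point but does not remove the defect, because the definition leaves the comparison open to it and the tables contain nothing that would reveal it.

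A reader might infer that the tables will show a difference, or that self-injection will look protective. The documents support neither. A protective appearance needs many reactions to end treatment. The large safety gap in the second set comes from following everyone for 364 days; adding the SAP's two longer cohorts roughly halves it (about -6 to about -3 points) and brings rejection to 6% to 7%.

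Dating is also imperfect. Under section 10.1, records from the third administration on are periods with a start date, a last date and an ongoing box. A tick on such a record does not show when within it the patient first self-injected, so the clean results with exact dates are a best case.

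**Conclusion.** The point holds conditionally. An ever-ticked flag is tabulated or tested as if fixed at the start, and nothing in the three tables corrects for it. If self-injection starts some time after the first dose, the tables can show differences when self-injection has no effect.

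- **Table 3.4** is then biased in favour of self-injection in every setting examined: about 3 to 7 points at a mean delay of 3 to 6 months, with rejection of 8% to 43% depending on delay and N.
- **Safety comparison** (Tables 2.5 and 2.9): either direction, about +7 to -7 points across both sets with mixed follow-up, close to zero in places. It depends on how many reactions end treatment and on the mix of 52-, 104- and 156-week cohorts. The false-positive concern is for Table 2.9 only, since Table 2.5 has no test.
- **Early switching:** rejection stays near 5% (3% to 7% with a mean delay of up to one month; 4% to 10% if complete by day 56).

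Because the safety bias has no predictable sign, a reader of the finished tables could not discount it.

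**What to change.** **Tables 2.9 and 3.4.** Remove self-administration from the tests. Alternatively, classify it at a fixed early landmark among patients still on the drug and count only later outcomes. The landmark costs the early stoppers in this one comparison; removal costs one screening result.

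**Table 2.5.** Assign each reaction to the mode of the administration record in force at onset, and use person-time in each mode as denominator. State that dating is approximate where one record covers a period. If that is not practical, keep the table and label it descriptive, not a comparison of the effect of self-injection.

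The cost is SAP wording and programming. The SAP already uses record start dates (section 10.1) and reaction onset dates (section 10.2). The survey sheet itself should be checked for how finely the tick can be dated.
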